## **OBJECTIVES:**

Aim: To evaluate the association between bolus volume and concentration of local anesthetic during maintenance of labor analgesia with programmed intermittent epidural bolus (PIEB) analgesia.

Hypothesis: Patients whose labor analgesia is maintained using PIEB with low-volume bolus (6.25 mL) of higher local anesthetic concentration solution (0.1% bupivacaine with fentanyl 2.0 mcg/mL) will have a longer duration of adequate analgesia (time to first manual re-dose request) than patients whose PIEB is delivered with a high-volume bolus (10 mL) of lower concentration local anesthetic solution (0.0625% bupivacaine with fentanyl 2.0 mcg/mL).

## **BACKGROUND:**

Neuraxial labor analgesia is performed by the administration of a local anesthetic/opioid mixture in the epidural space. The delivery method is a combination of continuous infusion, provider-administered boluses and patient-administered boluses (patient controlled epidural analgesia [PCEA]) via epidural catheter. Pain during the first stage of labor is primarily due to lower uterine segment and cervical stretching. The pain signals enter the spinal cord through sensory nerves at the T10 through L1 dermatomes. Pain signals from the late first stage and second stage of labor also arise from the vagina and perineum. These signals travel with the pudendal nerve and enter the spinal cord at S2-S4. Thus, the anesthetic solution administered through the lumbar epidural catheter must spread cephalad in the epidural space to reach the T10 nerve roots and spinal cord, and must spread caudad to reach the caudal nerve roots in the epidural space.

The optimal method for maintaining labor analgesia is unknown. Several studies have demonstrated that PIEB, in combination with PCEA, provide superior maintenance of labor analgesia (less need and longer time to provider intervention, lower local anesthetic consumption, less motor block, and improved patient satisfaction scores) than maintenance with a continuous infusion with PCEA.(1-4) The mechanism for this difference is not known; however, one suggested mechanism is improved spread of the local anesthetic within the epidural space. Kaynar *et al.* injected methylene blue dye through a multi-orifice catheter using either a continuous infusion or intermittent bolus and the area of diffusion was measured on a piece of paper.(5) The authors found that intermittent boluses were associated with a greater surface area of diffusion than continuous infusion. In a cadaver study, dye was injected into the lumbar epidural space, and cryomicrotome sections were taken.(6) Dye flowed in rivulets through small channels in the epidural space, as opposed to moving as a unified front. The authors found dye injected at high pressures had more uniform spread through the epidural space, supporting the concept of intermittent epidural injection providing superior analgesia.

Epidural infusion pumps capable of delivering PIEB of local anesthetic with PCEA have become commercially available and many studies have attempted to assess the optimal parameter settings (including volume of programmed bolus, bolus interval, rate of bolus administration) to provide superior labor analgesia. Recently we completed a double-blinded randomized control trial evaluating two bolus delivery rates, hypothesizing that those patients randomized to receive higher bolus delivery rates would have improved labor analgesia. However, no difference was found between groups.(7) What is more, both groups had a mean cephalad sensory level to cold of T6. This sensory level is higher than the traditional goal of T10 (upper dermatome level of uterine innervation), but despite the adequate sensory level, a large number of patients required

supplemental physician-delivered boluses of local anesthetic during labor. Forty percent of the women in the high-rate group and 36% of the low-rate group required a manual re-dose during labor.(7) This suggests that either a higher volume, or higher concentration of local anesthetic (i.e., higher dose) is needed to maintain adequate labor analgesia.

Traditionally higher concentration local anesthetic solutions have been associated with increased motor blockade leading to a higher incidence of instrumental vaginal delivery.(8) Several local anesthetic solutions with varying drug concentrations are available for labor analgesia and are used clinically in the United States. We plan to perform a randomized, controlled, double-blind study to test the hypothesis that patients whose labor analgesia is maintained using PIEB with low-volume bolus (6.25 mL) of a higher local anesthetic concentration solution (0.1% bupivacaine with fentanyl 2.0 mcg/mL) will require less supplemental analgesia (manual provider re-doses) than patients whose PIEB is delivered with a high-volume bolus (10 mL) of lower density local anesthetic solution (0.0625% bupivacaine with fentanyl 2.0 mcg/mL).

## **INCLUSION AND EXCLUSION CRITERIA:**

### **Inclusion criteria:**

Age: 18 years and above, nulliparous parturients who present to the labor and delivery unit for an induction of labor or who are in spontaneous labor, and request neuraxial labor analgesia at  $\leq 5$  cm cervical dilation are eligible to participate.

### **Exclusion criteria:**

Patients who are not eligible to receive a combined spinal epidural (CSE) technique with 25 mcg of intrathecal fentanyl, non-English speaking, failed initiation of CSE analgesia (VAS pain score  $>10$  15 minutes after intrathecal dose), need to have the epidural catheter replaced during labor, who deliver within 90 minutes of initiation of labor analgesia, or who require re-dose within 90 minutes of initiation of labor analgesia will be excluded from the study.

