## **MULTI-SITE RESEARCH: NA**

### **STUDY TIMELINES:**

The participants will be enrolled in the study at arrival, prior to request for labor analgesia. At the request for labor analgesia a vaginal exam will be performed by the obstetric or nursing team to ensure the patient still meets inclusion criterion. The patient will participate in the study from the time of initiation of combined-spinal epidural analgesia until the epidural catheter is discontinued after delivery. We estimate that it will take approximately 18 months to enroll 220 patients and perform data analysis.

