### **STUDY ENDPOINTS:**

**Primary outcome:** Need for supplemental physician-delivered bolus of local anesthetic.

**Secondary outcomes:** Time to first request for supplemental analgesia, total hourly bupivacaine consumption, mode of delivery, and motor block throughout labor and at 10 cm cervical dilation, sensory level throughout labor and at 10 cm cervical dilation, pain burden as defined as area under the pain-time curve, patient satisfaction.

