### **PROCEDURES INVOLVED:**

Parturients who meet the inclusion criteria will be approached by one of the investigators for study participation. Parturients who are willing to participate in the study will provide written consent. Patient demographics will be collected at study enrollment.

The research study team will determine group allocation by randomization via opaque sealed envelope. Participants will be randomized to one of two treatment groups based on a random computer-generated schedule (<https://www.randomizer.org>) and they will be blinded to the group to which they are assigned. The research study team will be blinded because the group will not be known other than group 1 or group 2 on the randomization card and on the pump. The CADD pump does not display the rate or the dose only group 1 or group 2.

Cervical dilation will be confirmed by a member of the obstetric team prior to initiation of CSE analgesia per routine practice. A baseline pain visual analog scale (VAS) score will be obtained using a 100-mm unmarked line with the end points labeled “no pain” and “worst pain imaginable.”

Labor analgesia will be initiated using CSE analgesia with 25 mcg of intrathecal fentanyl. An epidural test dose will be performed per routine (1.5% lidocaine with epinephrine 1:200, 3 mL).

Labor analgesia will be maintained using PIEB of local anesthetic with PCEA using the CADD-Solis pump (Smiths Medical). An unblinded anesthesia nurse will program the epidural pump and initiate the maintenance epidural infusion. The maintenance epidural solution for the high-

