volume, low-concentration group will be bupivacaine 0.625 mg/mL with fentanyl 2.0 mcg/mL with a PIEB volume of 10 mL and patient-controlled epidural analgesia (PCEA) volume of 8 mL. The maintenance epidural solution for the low-volume, high-concentration group will be bupivacaine 1 mg/mL with fentanyl 2.0 mcg/mL with a PIEB volume of 6.25 mL and PCEA volume of 5 mL. The PIEB volume will be administered every 45 minutes. The first bolus will be given 30 minutes after intrathecal injection, as has been done in previous studies at our institution.(7) The bolus delivery speed will be 250 mL/h in both groups, which is our current practice. In addition to the programmed boluses patients will be able to administer PCEA boluses can be delivered every 10 minutes with a maximum of three PCEA boluses in a one-hour period. Fifteen minutes following the intrathecal dose, a VAS score and a sensory level of analgesia will be obtained. The following information will be obtained every two hours until complete cervical dilation (10 cm): VAS pain score, sensory level, a modified Bromage score (0 - no motor paralysis; 1 - inability to raise extended leg, but able to move knee and foot; 2 - inability to raise extended leg and to move knee, but able to move foot; 3 - inability to raise extended leg or to move knee and foot).

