**Redoses:**

Up to three redoses of Bupivacaine .125% (10-15 mL) will be administered for inadequate pain control. The time to the first request for supplemental analgesia will be recorded on the study data sheet. The time, type and volume of bupivacaine used, and VAS scores before and 15 minutes after the re-doses will be recorded.

All other clinical management will be as per routine, and study participation will not interfere with anesthetic or obstetric care. Anesthesiologists will manage breakthrough pain in the usual manner (assessment of stage of labor and extend/density of neuraxial blockade, followed by the appropriate maneuver to reestablish adequate analgesia).

Following delivery, the patient will be asked to give one final VAS score and her overall satisfaction with labor using a 100 mm unmarked line (the left end labeled “not satisfied at all” and the right end labeled “extremely satisfied”). Mode of delivery, as well as the duration of the 1st and 2nd stage of labor, maximum oxytocin dose, maximum temperature recorded during labor, and any complaints for intrascapular pain will be recorded by study personnel.

Patient-Controlled Epidural Analgesia (PCEA) pump utilization data will be downloaded from epidural pumps after delivery. This will include the time to first PCEA request, the number of PCEA demands, the number of times that PCEA boluses were delivered, the total amount of local anesthetic consumed.

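### Catheter replacement during labor is listed as an exclusion although it almost always arises after randomization, so recorded primary events can be deleted

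*Combined protocol and SAP*

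**What the plan says.** The Exclusion criteria section lists, among several conditions, women who "need to have the epidural catheter replaced during labor". The sentence ends by stating the consequence for the whole list, with the last item reading "who require re-dose within 90 minutes of initiation of labor analgesia will be excluded from the study". The two neighbouring labor-course items (delivery and re-dose) carry a 90-minute limit; catheter replacement carries none.

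On timing, Study Timelines says: "The participants will be enrolled in the study at arrival, prior to request for labor analgesia". Procedures Involved says: "The research study team will determine group allocation by randomization via opaque sealed envelope". The moment of allocation is not given, but it must come before the pump is programmed. On the start of assigned treatment the same section says: "The first bolus will be given 30 minutes after intrathecal injection".

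The primary outcome in Study Endpoints is "Need for supplemental physician-delivered bolus of local anesthetic". The Redoses section leaves breakthrough pain to usual care, in which the block is assessed, "followed by the appropriate maneuver to reestablish adequate analgesia".

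Data and Specimen Management gives a censoring rule for the time outcomes. It covers cesarean delivery and women who never ask for supplemental analgesia, and does not mention catheter replacement. No section defines an intention-to-treat set, says how a replaced catheter is scored, or plans a sensitivity analysis for it.

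**The concern.** An eligibility criterion should be knowable before assignment. This one is usually met hours later, on a clinician's judgment about how well the catheter is working, so in effect it deletes women from the analysis after randomization.

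It can be linked to the outcome. A woman re-dosed at 3 hours whose catheter is replaced at 4 hours has already met the primary endpoint, and the rule then removes her.

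It can also be linked to the arm. The regimens differ in bolus volume (10 mL versus 6.25 mL) and in concentration, and both may affect the extent and density of block that the clinician assesses. Blinding does not cut this link, because a blinded clinician still responds to the block in front of him or her.

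If replacement is commoner in one arm and the replaced women are mostly failures, deletion makes that arm look better than it was. Recruiting 110 to obtain 91 protects power but does not protect against this selection.

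**Working it through.** **The plan's own figure.** Study-Wide Number of Participants assumes 40% versus 20% re-dose, power 0.8 and alpha 0.05. The two-sided comparison of two proportions needs 82 per group uncorrected and 91 with continuity correction, which matches the stated 91. Exact Fisher power at 91 per group is 80.8%. The allowance is 1 − 91/110 = 17.3%; its causes are not itemized. (Data and Specimen Management attaches other proportions to the same 91; that is a separate matter.)

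**Inputs for the bias check**
- From the documents: 110 recruited per arm; two-sided Fisher's exact test at 0.05.
- Assumed: a true re-dose rate of 30% in both arms, midway between the planned 40% and 20%; replacement proportion r in each arm; share s of replaced women who had been re-dosed. The documents give neither r nor s.

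**Formula.** After deletion, the analysed rate is (0.30 − s·r)/(1 − r) among about 110(1 − r) women. The rejection rate is the sum of the two binomial probabilities over all tables with p ≤ 0.05. For r = 2% and s = 1: (0.30 − 0.02)/0.98 = 28.6%, n = 108. For r = 8% and s = 1: (0.30 − 0.08)/0.92 = 23.9%, n = 101.

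| Replacement, 10 mL vs 6.25 mL arm | Re-dosed share s | Analysed rates | Spurious difference | Fisher | Chi-square |
|---|---|---|---|---|---|
| none | – | 30.0% vs 30.0% | 0 | 3.5% | 5.0% |
| 5% vs 5% | all | 26.3% vs 26.3% | 0 | 3.5% | 5.1% |
| 2% vs 4% | all | 28.6% vs 27.1% | 1.5 points | 4.8% | 5.7% |
| 2% vs 5% | all | 28.6% vs 26.3% | 2.3 points | 5.3% | 6.7% |
| 2% vs 8% | half | 29.6% vs 28.3% | 1.3 points | 4.6% | 5.7% |
| 2% vs 8% | 70% | 29.2% vs 26.5% | 2.7 points | 6.2% | 7.3% |
| 2% vs 8% | all | 28.6% vs 23.9% | 4.7 points | 10.7% | 12.1% |

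Swapping the arms (8% vs 2%) gives the same figures with the sign reversed. With 40% true failure in both arms, 2% vs 8% (all re-dosed) gives 8.2% by Fisher and 9.1% by chi-square.

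Part of the small Fisher rises is not bias. Fisher is less conservative when group sizes differ: with 108 and 101 women and 30% in both groups, the same enumeration gives 4.2%. The chi-square column, starting from 5.0%, isolates the bias better in the milder rows.

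**If the planned effect is real** (40% vs 20%, all replaced women being failures):
- 5% vs 5%: 0.35/0.95 = 36.8% and 0.15/0.95 = 15.8%, a difference of 21.1 points instead of 20.
- 2% vs 8%: 0.38/0.98 = 38.8% and 0.12/0.92 = 13.0%, a difference of 25.7 points.
- 8% vs 2%: 0.32/0.92 = 34.8% and 0.18/0.98 = 18.4%, a difference of 16.4 points.

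**The case against.** Several points can fairly be made for the plan.

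**Mechanism.** A reader might infer that poor spread is the mechanism under test, so that the rule deletes the failures of the small bolus and favours the hypothesis. The documents do not support this. Background says "one suggested mechanism is improved spread of the local anesthetic within the epidural space", but as an explanation of why programmed boluses do better than continuous infusion, and both arms here use programmed boluses. Background also reports that re-doses were common in the earlier trial although the mean sensory level was T6, and the sponsor expects the smaller volume to do better. What stands is narrower: the arms differ in features that may affect block quality, and sensory level is a secondary outcome. The direction is unknown.

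**Link to the outcome.** Redoses does not name catheter replacement among the responses to breakthrough pain, and no reason for replacement is given anywhere. Some replacements will be purely technical. That replaced women are mostly primary events is therefore an assumption, not a finding.

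**Size.** The 10.7% needs both a fourfold difference in replacement and every replaced woman already re-dosed. With milder assumptions the inflation is small, and with equal replacement there is none.

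**Timing.** Because the moment of allocation is not stated, a very early replacement could precede allocation or the first assigned bolus.

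**Separateness.** The same fault affects the 90-minute exclusions and the Study Drop Out rule. The 90-minute re-dose exclusion removes primary events by definition, whereas this one does so only sometimes.

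All of this limits the size and the wording. None of it supplies a rule that keeps a re-dosed woman's event once her catheter is replaced.

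**Conclusion.** The point holds. As written, the plan removes women for an event that almost always follows randomization, has no time limit, and may be related both to the outcome and to the assigned regimen. Nothing elsewhere in the documents offsets this.

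The size cannot be derived from the documents. Under the assumptions shown, the Fisher rejection rate runs from about 3.5% (no deletion or equal replacement) through 4.6% to 5.3% in mild cases to 10.7% in the severe case. The last figure should not be read as the expected error rate. With no true effect, the bias needs unequal removal between arms, and it can favour either. The defect is clear from the text, its magnitude is not, and the sponsor should correct it because the correction is cheap.

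**What to change.** 1. Remove catheter replacement from the Exclusion criteria and state that every randomized woman is analysed in her assigned group. Use the same set for time to first request.
2. In the primary analysis, count a woman as an event if she received a physician-delivered bolus at any time, or if her catheter was replaced for inadequate analgesia even without a prior bolus. Without the second part, a woman who went straight to replacement because of pain would be scored as a success.
3. Record the reason for each replacement and tabulate replacements by arm.
4. Report two sensitivity analyses: events defined by bolus only, and the analysis without replaced catheters.
5. Settle this together with the other post-randomization removals: the 90-minute exclusions and the Study Drop Out rule.

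The cost is a few lines of wording, one data field and one table row; clinical care is unchanged. Purely technical catheter failures will add a little noise, which the sensitivity analyses will show. The requirement of 91 per group stands if the 40% and 20% assumptions are kept for the widened event. If all 110 per arm are analysed at those rates, exact Fisher power is 87.9%.

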### **Study Drop Out:**

Subjects will be removed from the study if the Ob/Anesthesiologist determines there is a need to increase the concentration and volume of the local anesthetic solution.

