## **STUDY-WIDE NUMBER OF PARTICIPANTS:**

In a previous study in which 10 mL of a bupivacaine/fentanyl mixture was injected at 300 mL/h and 100 mL/hr, the duration to the first request for supplemental analgesia (manual bolus) was 356 minutes and 301 minutes with a 36% and 40% re-dose rate respectively.(7) We hypothesize that the group with low-volume bolus (6.25 mL) of greater density solution (0.1% bupivacaine with fentanyl 2.0 mcg/mL) will have fewer patients requiring supplemental analgesia than patients whose PIEB is delivered with a high-volume bolus (10 mL) of lower density local anesthetic (0.0625% bupivacaine with fentanyl 2.0 mcg/mL).

Assuming a 20% reduction in re-dose from 40% to 20%, a power of 0.8, and an alpha of 0.05, we estimate that we will need 91 patients per group. In order to account for drop-outs, we will recruit 110 patients per group.

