**DATA AND SPECIMEN BANKING: NA**

**DATA AND SPECIMEN MANAGEMENT:**

Group sample sizes of 91 in group 1 and 91 in group 2 achieve 80.276% power to detect a difference between the group proportions of 0.1250. The proportion in group 1 (the treatment group) is assumed to be 0.1250 under the null hypothesis and 0.2500 under the alternative hypothesis. The proportion in group 2 (the control group) is 0.1250. The test statistic used is

the two-sided Fisher's Exact Test. The significance level of the test is targeted at 0.0500. In order to account for drop-outs, we will recruit 110 patients per group.

Categorical data between groups will be compared using a chi-square or Fisher's exact test, and continuous data will be compared using a two-tailed t-test or Mann Whitney U test as appropriate. Time outcomes will be compared between groups using a Kaplan-Meier survival analysis technique with log rank test. Patients undergo a cesarean delivery or who do not request supplemental analgesia will be censored at the time of delivery. Labor pain will be calculated using the area under the VAS-time curve using the trapezium rule.

The subjects' identity will be guarded by assigning a numerical code, which is only known by the principal investigator. Data are stored in a department computer which is password protected. Each study subject will be assigned a study code number. The code will be used to link study data to patient identification (name) in a separate database. Subject data will be stored on secured computers at Northwestern University. Data access will be password-protected and only available to study investigators. The data forms will be de-identified after the chart review prior to analysis. 5 years after manuscript publication, both electronic and paper data will be destroyed using the current departmental standards.

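### Excluding patients re-dosed within 90 minutes removes primary-outcome events after the assigned regimen can have started, so the comparison can be biased in either direction

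*Combined protocol and SAP*

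**What the plan says.** Study Endpoints defines the primary outcome as "Need for supplemental physician-delivered bolus of local anesthetic", with no time window. The Exclusion criteria remove patients "who require re-dose within 90 minutes of initiation of labor analgesia will be excluded from the study", and also those who need the epidural catheter replaced or who deliver within 90 minutes. Study Drop Out adds: "Subjects will be removed from the study if the Ob/Anesthesiologist determines there is a need to increase the concentration and volume" of the solution. It does not say whether data collected before removal are kept.

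On timing, Study Timelines says: "The patient will participate in the study from the time of initiation of combined-spinal epidural analgesia". Under Procedures Involved, the pump is programmed by group before maintenance begins, and "The first bolus will be given 30 minutes after intrathecal injection", with repeats every 45 minutes. On allocation the same section says "The research study team will determine group allocation by randomization via opaque sealed envelope", without placing the opening of the envelope before or after the 15-minute VAS check.

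The analysis text, under Data and Specimen Management, names the tests and gives one censoring rule: "Patients undergo a cesarean delivery or who do not request supplemental analgesia will be censored at the time of delivery". It defines no analysis set and no sensitivity analysis for excluded or removed patients.

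**The concern.** A re-dose at 80 minutes is a primary-outcome event in a patient who has already received two programmed boluses of her assigned regimen. Under the Exclusion criteria she counts neither as an event nor in the denominator. The primary comparison is thus made only among patients selected for not having had the outcome early, and that selection happens after treatment has started. Randomisation does not protect such a comparison. If one regimen fails early more often, that regimen loses more events and looks better than it is.

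Time to first request is affected too. It is a secondary endpoint and also the basis of the hypothesis stated under Objectives. Apart from a request made shortly before 90 minutes and met after it, both Kaplan-Meier curves are held at 100% through 90 minutes by construction.

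The other exclusions that can follow assignment (catheter replacement, early delivery, removal under Study Drop Out) add to the problem, although the point does not depend on them.

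**Working it through.** **1. Does assigned treatment precede the cut-off?** The first programmed bolus is at 30 minutes and the second at 30 + 45 = 75 minutes; both are before 90. The pump has to be programmed by group before the first bolus, so allocation precedes it whenever the envelope is opened.

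**2. Can the direction be predicted from dose?** No. Bupivacaine per programmed bolus is 10 mL × 0.625 mg/mL = 6.25 mg and 6.25 mL × 1 mg/mL = 6.25 mg. Per patient-controlled bolus it is 8 × 0.625 = 5 mg and 5 × 1 = 5 mg. The arms differ in volume and concentration, not in mass per bolus.

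**3. The plan's own figure.** Study-Wide Number of Participants assumes re-dose rates of 40% and 20%, power 0.8 and alpha 0.05. Two-sided, without continuity correction:

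n₀ = [1.960·√(2·0.3·0.7) + 0.842·√(0.4·0.6 + 0.2·0.8)]² / 0.2² = 81.2, so 82.

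With continuity correction: n = (n₀/4)·[1 + √(1 + 4/(n₀·0.2))]² = 90.95, so 91. The stated 91 per group reproduces. Exact two-sided Fisher power is 80.8% at 91 per arm and 87.9% at the 110 recruited. (Data and Specimen Management gives a different pair of rates, 12.5% and 25%. That is a separate matter and is not used here.)

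**4. Effect of the exclusion.** Let p be the re-dose rate among all patients in an arm and f the share removed, all of whom had the event. The analysed rate is (p − f)/(1 − f), and the analysed number is 110·(1 − f), rounded. For example, p = 0.40 and f = 0.10 gives 0.30/0.90 = 33.3% with n = 99. The values of f are assumptions; the documents give none.

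True rates 40% (low concentration) vs 20% (high concentration). The last column applies the same analysed rates with exactly 91 analysed per arm:

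| Removed, low / high conc. | Analysed rates | Risk ratio | Power, from 110 per arm | Power, 91 analysed |
|---|---|---|---|---|
| none | 40.0% vs 20.0% | 0.50 | 88% | 81% |
| 5% / 2.5% | 36.8% vs 17.9% | 0.49 | 85% | 78% |
| 10% / 5% | 33.3% vs 15.8% | 0.47 | 82% | 75% |
| 10% / 3% | 33.3% vs 17.5% | 0.53 | 72% | 64% |
| 10% / 10% | 33.3% vs 11.1% | 0.33 | 96% | 94% |
| 5% / 10% | 36.8% vs 11.1% | 0.30 | 99% | 98% |

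Equal overall rates of 40% in both arms:

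| Removed, arm A / arm B | Analysed rates | Rejection, from 110 per arm | Of which favouring A | Rejection, 91 analysed |
|---|---|---|---|---|
| none | 40.0% vs 40.0% | 3.4% | half | 3.6% |
| 5% / 5% | 36.8% vs 36.8% | 3.7% | half | not run |
| 10% / 10% | 33.3% vs 33.3% | 3.6% | half | 3.5% |
| 10% / 5% | 33.3% vs 36.8% | 7.3% | 6.8 points | 5.9% |
| 15% / 5% | 29.4% vs 36.8% | 17.4% | 17.3 points | 14.9% |

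All power and rejection figures are two-sided exact Fisher at alpha 0.05.

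**The case against.** The trial is about maintenance of analgesia, and the rule probably aims to screen out failed initiation or a faulty catheter. Clinicians and research staff are to be blinded. However, failed initiation and catheter replacement already have their own criteria, while the re-dose criterion names no cause and so also removes patients for whom the assigned regimen was inadequate. Blinding limits differences that come from knowing the arm; it does not limit differences that the regimens cause.

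The objections to the size of the effect have more force. If early failures follow the planned 2:1 ratio, power from 110 per arm stays above 80%. Removing 10% from the 20% arm supposes that half of that arm's events come before 90 minutes, which nothing in the documents supports. The false-positive figures need early and late effects that cancel: at 15% / 5%, the later re-doses are 25% and 35% of those randomised, so the regimens really do differ after 90 minutes, in the opposite direction. The 17% is therefore an extreme case. Starting from 110 also ignores other losses, hence the 91-analysed columns.

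These points limit what can be said about size. They do not alter the fact that the primary comparison is conditioned on its own outcome.

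**Conclusion.** The concern holds and should be fixed before analysis. As written, the plan deletes primary-outcome events that occur on assigned treatment, and nothing in the analysis text restores them. Confidence is high on that structural point.

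The size and direction of the bias cannot be known from the documents. Over the assumed removals from 110 per arm, the risk ratio of 0.50 moves to between 0.30 and 0.53, and power to between 72% and 99%. False rejection rises above 5% only if early failure differs by arm while overall rates are equal. If early failure is equal, error is preserved but the effect estimated is not the one planned (0.33 instead of 0.50 at 10% / 10%).

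The documents do not say whether the prior study's 40% already left out early re-doses. If it did, the planning rates are net of them and the power loss does not follow; the conditioning on the outcome remains.

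**What to change.** - **Primary analysis set:** all randomised patients whose study pump was started, in the assigned arm. Count any physician-delivered re-dose after pump start as an event, including those within 90 minutes. Use the same set for time to first request.
- **Randomisation time:** state that the envelope is opened after the 15-minute VAS check, so that failed CSE is settled before allocation. List by arm any patient randomised whose pump was not started, and any re-dose between allocation and pump start.
- **Other occurrences after assignment:** keep patients with catheter replacement, delivery within 90 minutes or removal under Study Drop Out in the set, with outcome data collected to delivery. Without a physician re-dose they are non-events, as the endpoint is worded.
- **Sensitivity analyses:** first, apply the present exclusions and removals; second, count a Study Drop Out removal without a prior re-dose as an event.
- **Reporting:** give the number and reason for each of these occurrences by arm.

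The endpoint and clinical care are unchanged. The cost is analysis-set wording, a stated envelope time, and continued outcome collection after removal. On the plan's 40% vs 20%, 110 per arm gives 88% power with everyone kept, so no increase in sample size is needed; that rests on those rates applying once early re-doses are counted. The downside is that some early catheter failures unrelated to the regimen will add noise to the primary outcome.
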